5.2.3 Justification for Inclusion of IV tPA Failures

IV tPA has a short plasma half-life and its ability to revascularize large clot burdens is negligible. The recanalization rates of IV tPA for proximal arterial occlusions ranges from

Document Number: CDM10000146

Rev: AD

only 10% for internal carotid artery (ICA) occlusions to 30% for proximal middle cerebral artery (MCA) occlusions. [76]

In earlier time windows it has been shown that combining IV tPA with neurothrombectomy does not substantially increase the risk of symptomatic intra-cerebral hemorrhage or other complications over that of neuro-thrombectomy alone. [77]

In subjects who are eligible, IV tPA should be administered as per the labeled indication and local practice guidelines, as this is considered best medical practice, and it should not be withheld from those who are eligible. However, if symptoms persist beyond 60 minutes after completion of IV tPA administration, and the presence of an intracranial ICA or MCA-M1 occlusion is confirmed by CTA/MRA, then the subject may be considered for eligibility in this trial.

If a subject presents to the participating site after having received IV tPA at an outside hospital, the participating site must repeat all relevant assessments, including the baseline NIHSS and CTA/MRA to confirm the presence of an occlusion in the intracranial ICA or MCA-M1, in order to qualify the subject as a potential candidate for participation in the trial. If the subject continues to meet all inclusion and none of the exclusion criteria they may be randomized and enrolled.

5.2.4 Justification for Non Reliance on Penumbra Imaging

Several studies have been reported in the literature demonstrating the general safety and effectiveness of using the ratio of "core infarct" to "salvageable penumbra" concept to select patients for reperfusion therapies. The methods of measuring and/or defining "core infarct" and "salvageable penumbra" however vary from study to study. [31, 37, 42, 78-83]

In DEFUSE 2, which included subjects within 12 hours from symptom onset, those with a "target mismatch" (favorable ratio of salvageable penumbra to infracted core tissue) who were reperfused, had an increased rate of good outcomes at 90 days compared to those who were not reperfused (57% vs. 31%). SICH rates were 7% vs. 19% respectively, suggesting that a randomized controlled trial of endovascular treatment for subjects with a target mismatch profile is warranted, [84] and does not expose subjects to an excessive risk of SICH.

The MR RESCUE trial used DWI-PWI mismatch to identify favorable penumbral patterns versus non-favorable penumbral patterns in subjects enrolled into the trial. Surprisingly, the trial failed to show a differential benefit of endovascular intervention among favorable penumbral pattern subjects. [59] However, the results are not definitive, given the small sample size, large core lesions at baseline, and modest rates of substantial recanalization. The results also raise the question of the validity of relying upon perfusion measurements to identify salvageable penumbra, as the perfusion study parameters used to categorize

Document Number: CDM10000146

favorable versus non favorable penumbral patterns in this trial failed to predict how much infarct growth would occur in the absence of reperfusion.

The STAIR VIII consensus statement recommends that in addition to vessel imaging to confirm large artery occlusion, full-scale penumbral imaging *should be* employed to select patients for possible inclusion into randomized therapy trials in the 8-24 hour timeframe, given the high proportion of subjects with already-completed infarcts. [75] However, there is no consensus in the literature on what the correct imaging modalities, maps or thresholds are for determining the extent of salvageable penumbra versus benign oligemia, versus already infarcted tissue. [85-86] Perfusion imaging is not yet a consistently reliable means of identifying salvageable penumbra. [87]

5.2.5 Justification for Use of Clinical Imaging Mismatch Criteria

Some data show that infarct core volume is a better predictor of outcomes than perfusion based imaging selection. [38, 88-89] DEFUSE 2 pre-procedure infarct volume along with age were the only independent predictors of outcome and core infarct volumes of less than or equal to 15 cc is the best discriminator of good versus bad outcome. Perfusion MR in addition to DWI did not add anything to this model. [90] In another retrospective analysis of 201 endovascularly treated patients, age and final infarct volume were found to be independent predictors of outcome. [91]

However, because patients with small core infarcts tend to do well even without treatment it is possible that infarct core by itself may not demonstrate a significant difference in outcomes between treated and a matched cohort of control subjects. The larger the mismatch between infarct core measurement and salvageable penumbra the greater the treatment effect is likely to be with reperfusion therapy, and the more substantial the infarct growth is likely to be without reperfusion therapy. No mismatch signals that the subject is not going to grow their infarct and thus will not benefit from reperfusion. [78, 82]

A Clinical Mismatch is the difference between the expected neurological deficits and the actual neurological deficits observed on examination of a patient, by National Institutes of Health Stroke Scale (NIHSS) in comparison to their occlusion location and size of core infarct. In the presence of small core infarct and confirmed LVO, baseline NIHSS appears to be a reliable indicator of "at risk" tissue. [87]

Patients with a low baseline NIHSS are likely to do well even in the presence of large vessel occlusion and no reperfusion therapy. In PROACT II there was a minimal treatment effect for M1 occlusions in the NIHSS 4-10 and a negative treatment effect for M2 occlusions in this same group (the control group did better). Larger treatment effects were noted both for M1 occlusions and M2 occlusions in the NIHSS 11-20 strata. [92]

Document Number: CDM10000146

Higher baseline NIHSS scores are generally well correlated with more proximal LVOs. In one study, NIHSS scores ≥ 10 demonstrated a positive predictive value for arterial occlusions in 97% of carotid and 96% of vertebrobasilar strokes. [93] In the EMS pilot study there was a significant correlation between the baseline NIHSS and the likelihood of presence of clot on initial angiography. All patients with a baseline NIHSS ≥ 15 and 44% of patients with NIHSS of 10 to 14 had appropriate clots. [94]

For subjects with a core infarct volumes between 0 and 30 cc, a baseline NIHSS cutoff of ≥ 10 was chosen to define the clinical imaging mismatch because it is thought to be a reasonable predictor of likely progression of stroke and/or poor outcome in the absence of reperfusion. [95]

For subjects with larger core infarct volumes, above 30 cc but less than 50 cc, a baseline NIHSS cutoff of \geq 20 was chosen to define the clinical imaging mismatch, based upon this same subgroup of subjects in IMS III. Though not statistically significant at the p=0.05 level, the group treated with endovascular therapy had a higher rate of good clinical outcomes compared to the IV tPA group (23.8% versus 16.8% respectively). [58]

Stricter inclusion criteria are defined for subjects greater than 80 years of age. In one study of IV tPA treated patients, the overall rate of symptomatic ICH (SICH) in the octogenarians was 6.9%, compared with 5.3% in younger patients. The use of MRI to select octogenarians for thrombolytic therapy seemed to decrease the risk of SICH, but did not influence the overall outcome after 3 months. [96] In another published study comparing outcomes in IV tPA treated and non-treated subjects \geq 80 and < 80 years old, although age was associated with poorer outcomes the association between thrombolysis treatment and improved outcomes was maintained in the very elderly subjects, and their conclusion is that age alone should not be considered a barrier to treatment.[97] However, in order to mitigate the potential risks associated with endovascular treatment in the elderly as well as to maximize the chance of a good outcome, the core infarct volume in subjects who are \geq 80 years will be restricted to \leq 20 cc.

In the absence of a "gold standard" to define salvageable penumbra, DAWN subject selection is based on a Clinical Imaging Mismatch using standardized collection and post processing of MRI-DWI or CTP-rCBF maps to calculate core infarct volumes, across all study sites.

A Clinical Imaging Mismatch is the observed difference between the size of the core infarct and the magnitude of the neurological deficit, in the presence of confirmed LVO by CTA/MRA, and appears to be a reliable and efficient surrogate for assessing salvageable penumbra. [87] Using this method we aim to select subjects at risk of further infarct growth without rapid reperfusion.

Document Number: CDM10000146

Based upon the above justifications, there are three distinct Clinical Imaging Mismatch subgroups defined in DAWN:

- a. 0-<21 cc core infarct and NIHSS ≥ 10 (and ≥ 80 years old)
- b. $0 \le 31$ cc core infarct and NIHSS ≥ 10 (and ≤ 80 years old)
- c. 31 cc to <51 cc core infarct and NIHSS ≥ 20 (and < 80 years old)

5.2.6 Justification for Use of Standardized Core Infarct Imaging Software

In order to select subjects who are most likely to benefit from mechanical thrombectomy and less likely to be harmed by it, the inclusion criteria are limited to subjects with core infarct volumes between 0-50 cc. In DAWN, core infarct volume measurements will be standardized using a validated, FDA-cleared software platform for measuring core infarct (RAPID software, iSchemaView, Palo Alto, CA, or alternatively Olea Sphere, Olea, Cambridge, MA)

Diffusion/perfusion imaging software for core infarct assessment is 510(k) cleared in the United States, and has been/is being used in several global stroke trials to date, including DEFUSE, DEFUSE 2, EXTEND, EXTEND IA, CRISP, and SWIFT PRIME. The software takes DICOM images acquired on a variety of CT or MR scanners and uses an automated algorithm to post-process the resulting ADC maps (MRI-DWI) or r-CBF maps (CTP) in order to consistently measure core infarct volumes. All raw data/maps will be visible to the treating physician such that if an artifact or error is suspected the scans can be assessed visually to confirm that the patient is appropriate for enrollment.

The CT/MR Core Lab will verify, and record, the core infarct volumes generated by the software as well as "cleaned" volumes following removal of any artifact. The core lab will also provide timely feedback to the study sites regarding quality control issues.

Since it is recognized that any image of the brain is a "snapshot in time", DAWN requires that the corresponding clinical "mismatch" be evaluated using the baseline NIHSS obtained within 1 hour of the processed images used to qualify the subject for the study.

Though MRI-DWI is the preferred method to measure the core infarct volume, due to logistic barriers such as unavailability of MRI equipment or technicians, and subject contra-indications for MR, sites are permitted to use either MRI-DWI or CTP-rCBF to measure the core infarct volume.

5.2.7 Justification for Use of Weighted mRS as Primary Endpoint Analysis

The primary endpoint is 90-day clinical outcomes assessed by the modified Rankin Scale (mRS), analyzed using both the average weighted mRS categories (weighted mRS

Document Number: CDM10000146

Rev: AD

analysis) and proportions of subjects with good functional independence (mRS 0-2) (dichotomous analysis).

It is possible that widespread use of dichotomized outcome scales can potentially lead to the discarding of important information about treatment effects. Analysis over ranks, taking into account all assessed gradations of outcome along the disability spectrum, provides a more comprehensive assessment of intervention effects and has been recommended by both the US and European consensus expert groups on trial design. [98-99]

An important advancement is the development of utility values for each level of the modified Rankin Scale of global disability. [75] Weighting the seven Rankin levels by utilities further improves the precision of the scale as a measure of disability, converting the scale from a somewhat arbitrary fixed interval instrument to a measure with rank distances that directly reflect patient and society valuation of outcome health states. Formal derivations of utility values for each Rankin grade has recently been completed by two groups, using patient informants from a population-based study and using health professional informants following the World Health Organization Global Burden of Disease methodology. [48,49] Both methods yielded similar values, which were averaged to derive the utility-weighted Rankin Scale used in this trial. Use of a utility-weighted Rankin Scale permits a trial to capture all the effects a treatment can have on a subject to the degree each is important to the subject and society [104].

5.2.8 Justification for Use of Adaptive Design

The combined feasibility / pivotal design increases trial efficiency, allowing the study to be stopped early if there is no evidence of a meaningful treatment effect, or allowing it to continue if a meaningful treatment effect is perceived after the first interim analysis. The adaptive design allows for early and frequent interim analyses so that rather than waiting until the maximum number of subjects have been enrolled, decisions about stopping early for either predicted success or failure, are made based on pre-specified rules and patients are spared from unnecessary randomization.

The adaptive design also allows for refinement of the target population to smaller infarct sizes based on the data that accumulates during the course of the trial, thereby sparing the randomization of future subjects who are unlikely to benefit from the treatment. Refer to **Appendix F**, which contains the Adaptive Design Plan, prepared by Berry Consultants.

Currently there is clinical equipoise to randomize subjects between these two arms because there is no evidence of improved clinical outcome in patients who are treated either way within 6-24 hours from time last seen well. Adaptive trial design techniques may be helpful in identifying subgroups of subjects with enhanced treatment benefit and delineating the thresholds at which benefits fade. Several biomarkers have been identified that are hypothesized to identify patients with substantially increased benefit from neurothrombectomy, including infarct core size, presence of salvageable penumbra, etc. A

Document Number: CDM10000146

Bayesian adaptive trial design permits information gained about subgroups collected within the trial to modify enrollment criteria as the study progresses. [100] The core volume threshold at which benefit no longer accrues, if one exists, is likely to be most efficiently identified by using adaptive modification of trial entry criteria. [75]

5.3 Method of Assigning Subjects to Treatments

Randomization will be accomplished at each site using either a block of randomization envelopes, or by using a commercially available Interactive Voice Response System (IVRS) or Interactive Web Response System (IWRS). Subjects will be randomized 1:1 to Trevo thrombectomy plus medical management or medical management alone. In order to ensure both groups are balanced, subjects will be stratified by Clinical Imaging Mismatch (CIM) subgroups (see Imaging Inclusion Criteria in **Section 6.1.1**), TLSW between 6 and ≤ 12 hours and >12 to 24 hours, and baseline occlusion location (ICA vs. M1). Enrollment in this study is defined as the moment when the randomization process is completed and the subject is assigned to a study arm. After randomization, no crossover is permitted.

5.4 Blinding and Breaking the Blind

This protocol is designed as an open label treatment assignment. The presence or absence of hemorrhage will be determined by the CT/MR core lab which is blinded to each subject's group assignment. Core infarct volume at baseline will be measured by automated calculations, using standardized software at each participating site. Review of all images and calculations will be conducted by the CT/MR core lab on an ongoing basis as images are collected (within 72 hours will be the goal), and feedback will be provided to the sites to ensure that the Core Infarct volumes are not impacted by artifacts or equipment upgrade issues at the site. The Angiographic Core Lab assessing angiograms for revascularization/reperfusion will not be blinded, as this evaluation will only be made for subjects in the Trevo Thrombectomy plus medical management arm.

Each site must designate one or more individual(s) to perform the blinded mRS assessments at Day 5-7 or discharge (whichever is earlier), Day 30 (\pm 14) and Day 90 (\pm 14). This individual will be identified on the Delegation of Authority Log, and must not perform data entry or other tasks that would reveal the study arm assignment of subjects. Moreover, the blinded evaluator(s) will be instructed to follow a scripted interview to minimize the chance of subjects disclosing their treatment group to the evaluator, and will also be required to self-certify that they remained blinded throughout the interview with the subject. If the blind is broken for any reason, this will be documented on the data collection forms.

[Remainder of page is intentionally blank.]

Document Number: CDM10000146

6 Study Population

6.1 Inclusion Criteria

General Inclusion Criteria	 Clinical signs and symptoms consistent with the diagnosis of an acute ischemic stroke and subject belongs to one of the following subgroups: a. Subject has failed IV t-PA therapy (defined as a confirmed persistent occlusion 60 min after administration) b. Subject is contraindicated for IV t-PA administration Age ≥18 Baseline NIHSS ≥10 (assessed within one hour of measuring core infarct volume) Subject can be randomized between with 6 to 24 hours after time last known well No significant pre-stroke disability (pre-stroke mRS must be 0 or 1) Anticipated life expectancy of at least 6 months Subject or subject's Legally Authorized Representative (LAR) has signed the study Informed Consent form* * If approved by local ethics committee and country regulations, the investigator is allowed to enroll a patient utilizing emergency informed consent procedures if neither the patient nor the representative or person of trust is available to sign the informed consent form. However, as soon as possible, the patient is informed and his/her consent is requested for the possible continuation of this research. (Not applicable to U.S. Sites.) 	
General Inclusion Criteria (additional information)	 Subjects receiving heparin or low molecular weight (LMW) heparin e.g. Fragmin® (Dalteparin Sodium) or an intravenous direct thrombin inhibitor such as Angiomax® (Bivalirudin), or Argatroban within the last 24 hours from screening are eligible for participation if their coagulation profile remains acceptable. Subjects on factor Xa inhibitors (e.g. apixaban) or direct thrombin inhibitors are eligible for participation 	
Imaging Inclusion Criteria	 < 1/3 MCA territory involved, as evidenced by CT or MRI Occlusion of the intracranial ICA and/or MCA-M1 as evidenced by MRA or CTA Clinical Imaging Mismatch (CIM) defined as one of the following on MR-DWI or CTP-rCBF maps: a. 0-<21 cc core infarct and NIHSS ≥ 10 (and age ≥ 80 years old) b. 0-<31 cc core infarct and NIHSS ≥ 10 (and age < 80 years old) c. 31 cc to <<51 cc core infarct and NIHSS ≥ 20 (and age < 80 years old) 	

6.2 Exclusion Criteria

General Exclusion Criteria	 History of severe head injury within past 90 days with residual neurological deficit, as determined by medical history Rapid improvement in neurological status to an NIHSS <10 or evidence of vessel recanalization prior to randomization Pre-existing neurological or psychiatric disease that would confound the neurological or functional evaluations, e.g. dementia with prescribed anti-cholinesterase inhibitor (e.g. Aricept) Seizures at stroke onset if it makes the diagnosis of stroke doubtful and precludes obtaining an accurate baseline NIHSS assessment
	5. Baseline blood glucose of <50mg/dL (2.78 mmol) or >400mg/dL (22.20 mmol)
STRYKER CONFIDENT	IAL - THIS DOCUMENT CONTAINS CONFIDENTIAL AND PROPRIETARY INFORMATION THAT

Document Number: CDM10000146

	 Baseline hemoglobin counts of <7 mmol/L (11.28 g/dL) Baseline platelet count < 50,000/uL Abnormal baseline electrolyte parameters as defined by sodium concentration <130 mmol/L, potassium concentration <3 mEq/L or >6 mEq/L Renal failure as defined by a serum creatinine >3.0 mg/dL (264 µmol/L) NOTE: subjects on renal dialysis may be treated regardless of serum creatinine levels Known hemorrhagic diathesis, coagulation factor deficiency, or on anticoagulant therapy with INR > 3.0 or PTT > 3 times normal. NOTE: Patients on factor Xa inhibitor within 24-48 hours must have PTT within 3 times normal. Any active or recent hemorrhage within the past 30 days History of severe allergy (more than rash) to contrast medium Severe, sustained hypertension (Systolic Blood Pressure >185 mmHg or Diastolic Blood Pressure >110 mmHg) NOTE: If the blood pressure can be successfully reduced and maintained at the acceptable level using medication the subject can be enrolled Female who is pregnant or lactating at time of admission Current participation in another investigational drug or device study Presumed septic embolus, or suspicion of bacterial endocarditis Treatment with any cleared thrombectomy devices or other intra-arterial (neurovascular) therapies prior to randomization
Exclusion Criteria (additional information)	 The "correction" of baseline glucose or coagulation laboratory values to meet inclusion criteria will not be allowed. Subjects who have taken Clopidogrel, aspirin, or both within the last 24 hours from screening for the trial should not be excluded if their coagulation profile remains acceptable. Subjects with a questionable seizure at onset of stroke should not be excluded if CTA/MRA confirms the presence of intracranial ICA and/or M1 occlusion, and accurate NIHSS can be obtained.
Imaging Exclusion Criteria	 Evidence of intracranial hemorrhage on CT/MRI CTA or MRA evidence of flow limiting carotid dissection, high-grade stenosis, or complete cervical carotid occlusion requiring stenting at the time of the index procedure (i.e., mechanical thrombectomy). Excessive tortuosity of cervical vessels on CTA/MRA that would likely preclude device delivery/deployment Suspected cerebral vasculitis based on medical history and CTA/MRA Suspected aortic dissection based on medical history and CTA/MRA Intracranial stent implanted in the same vascular territory that would preclude the safe deployment/removal of the Trevo device Occlusions in multiple vascular territories (e.g., bilateral anterior circulation, or anterior circulation/vertebrobasilar system) as confirmed on CTA/MRA, or clinical evidence of bilateral strokes or strokes in multiple territories Significant mass effect with midline shift as confirmed on CT/MRI Evidence of intracranial tumor (except small meningioma) as confirmed on CT/MRI

Document Number: CDM10000146

6.3 Withdrawal and Replacement of Subjects

While study withdrawal is discouraged, subjects may withdraw from the study at any time, with or without reason and without prejudice to further treatment. Withdrawn subjects will not undergo any additional follow-up, nor will they be replaced.

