6.4 Enrollment Controls

Enrollment will be monitored to ensure that no more than the maximum planned number of subjects is enrolled. An electronic data capture system will be used, and the system will be set to automatically notify the CRA or Project Manager of all subject enrollments being entered within the system. As enrollment nears the maximum allowed one of two methods will be employed to notify sites of status of enrollment:

1. If an automated randomization system is utilized, sites will be notified via automatic preprogrammed notifications within the IVRS/IWRS system, when they attempt to randomize a patient, specifically when enrollment is no longer available.

2. If randomization envelopes are utilized, the Project Manager or designee will monitor the enrollment status daily (when enrollment is within 10 subjects of the maximum allowed enrollment) and send out an e-mail requesting sites to call a specific telephone number or e-mail a designated person to ask permission before randomizing and enrolling a subject.

7 Study Procedures

The schedule of events is the same for all subjects in the trial except those subjects randomized to the Trevo plus Medical Management arm will undergo an intra-arterial Trevo thrombectomy procedure. All subjects who are enrolled into the trial will be followed for 90 days (\pm 14) unless they withdraw early from the trial, expire before the 90 day follow up window is reached, or are lost to follow up. The Time and Events schedule is outlined in Table 5.

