4.8. Eligibility of Subjects, Exclusions, and Missing Data

Based on previous experiences in clinical trials of acute stroke, minimal loss to follow-up (LTFU) is expected for the 90-day assessment of the primary outcome measure. In the MERCI study, 7.2% (11/151) of subjects were LTFU, in Multi MERCI 2.4% (4/164) were LTFU, and in the TREVO 2 study, 3.4% (6/178) were LTFU. All efforts should be made to ensure near complete follow-up, with particular focus on the assessment of the primary outcome (mRS at 90 days) and mortality.

Nevertheless, some missing data may still occur. All randomized subjects will be included in the primary endpoint analysis (ITT). In case of missing 90-day mRS values, the 30-day mRS values will be incorporated into a multiple imputation model. In case of missing 90-day and missing 30-day mRS values, multiple imputation models will incorporate the day 5-7mRS; if that also missing, the subject will be counted as a failure (mRS 6). For conventional statistical analysis of the 90 day mRS and descriptive statistics (e.g. distribution of of mRS) will use LOCF of 30 day data. Refer to the adaptive design plan for details in Appendix F of study protocol.

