4.9. Population Definitions

Screened: Includes any subject who is considered for participation for the trial, whether or not they sign an informed consent.

Screen-failed: Includes any subject who is considered for participation for the trial, who either fail to meet one or more of the inclusion criteria or who meet one or more of the exclusion criteria; subjects can be screen failed based on general inclusion/exclusion criteria, or imaging inclusion/exclusion criteria (these subjects may or may not have signed an informed consent).

Enrolled: Includes any subject who has been randomized based upon the results of the RAPID post-processing of the baseline MRI-DWI or CTP-rCBF baseline images, and Clinical Imaging Mismatch profile (informed consent must be obtained prior to randomization).

Completed: Includes any subject who is enrolled/randomized and completes the study follow up at Day 90 (± 14), or is known to have expired before 90 days post randomization.

Discontinued: Includes any subject who is enrolled/randomized but who fails to complete the study follow up at Day 90 (± 14), and who has not expired before 90 days post randomization.

Wake-up Strokes: Subjects known to have symptoms first detected on awakening from sleep.

Witnessed Strokes: Subjects with last known well time and symptoms first observed time known to be the same.

Un-witnessed Strokes: Subjects with last known well time and symptoms first observed time known to be different, but not known to have symptoms first detected on awakening from sleep.

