4.11. Estimated Duration of Subject Participation

Subjects will be followed for 90 (± 14) days post-procedure, with data collection 24(-6/+24) hours post randomization, on the day of hospital discharge or 5 to 7 days (whichever occurred sooner), 30 days (± 14 days), and 90 days (± 14 days) post-procedure. Subjects who do not withdraw prematurely from the study will be followed for a maximum of 104 days following the study procedure. Any subject who discontinues from the study for any reason will be followed to monitor safety for the duration of the study. If a subject withdraws from the study with an existing adverse event, regardless of the relationship to the study device or procedure, the subject will only be followed for a maximum of 104 days following their study procedure date.

Stryker Neurovascular

Document Title: DAWN™ Trial Statistical Analysis Plan

Document Number: CDM10000704

Rev: AB

TABLE 2. DAWN STUDY TIME AND CLINICAL ASSESSMENT SCHEDULE

Event	Screening/ Baseline	Procedure (Treatment Arm Only)	24 Hr (-6/+24) (post randomization)	Day 5-7 / Discharge (whichever is earlier)	Discharge	Day 30 ± 14	Day 90 ± 14
Inclusion/Exclusion Criteria	✓						
Demographics/Medical History/Baseline Medications	✓						
Baseline Characteristics	✓						
Baseline Labs	✓						
Informed Consent	✓						
Randomization (t=0)	✓						
Angiography Procedure Details (Treatment Arm only)		✓					
mRS [†]	✓ (pre stroke)			✓ [†]		✓ [†]	✓ [†]
NIHSS	✓ [*]		✓ ^{**}	✓		✓	✓
Neuro imaging (to assess for hemorrhage, occlusion location/vessel patency & infarct volume)***	✓ MR-DWI/MRA or CT/CTA/CTP		✓ MR-DWI/MRA or CT/CTA	✓ MR-DWI or CT (optional)			
AEs/SAEs (from time of randomization)		✓	✓	✓		✓	✓
Concomitant Medications		✓	✓	✓		✓	✓
In Hospital Med Management					✓		
Intubation Details					✓		
UB04					✓		

*NIHSS should be obtained within 1 hour of corresponding core infarct measurement.

** NIHSS should be obtained within 2 hours of the 24 (-6/+24) hour neuro-imaging to determine presence/absence of hemorrhage. [†] Must be conducted by an individual blinded to the treatment arm.

*** CT/MR and Angiographic images should be de-identified before being submitted to Stryker NV or core lab.

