6.3. Rules for Calculating Rates and Handling Denominators

For Safety events, binary rates will be calculated using as a denominator as the number of all Subjects in the study, regardless of their follow-up time.

Stryker Neurovascular

Document Title: DAWN™ Trial Statistical Analysis Plan

Document Number: CDM10000704

Rev: AB

Other binary rates such as mRS or NIHSS will be calculated using a denominator as the total number of the available data for the outcome, excluding missing values.

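### Protocol 6.3 ends all follow-up at withdrawal while SAP 4.11 continues it for safety; if the protocol rule is applied, Day-90 mRS and later deaths go unobserved and 90-day stroke-related mortality could be understated

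*Protocol*

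**What the plan says.** On follow-up after withdrawal, the documents give two rules.

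- Protocol 6.3: "Withdrawn subjects will not undergo any additional follow-up, nor will they be replaced". The opening paragraph of Protocol Section 7 agrees: subjects are followed for 90 days "unless they withdraw early from the trial, expire before the 90 day follow up window is reached, or are lost to follow up".
- SAP 4.11: "Any subject who discontinues from the study for any reason will be followed to monitor safety for the duration of the study". The next sentence deals with a subject who withdraws with an existing adverse event and says "the subject will only be followed for a maximum of 104 days following their study procedure date".
- SAP 4.9 (and Protocol 8.4) define a discontinued subject: "Includes any subject who is enrolled/randomized but who fails to complete the study follow up at Day 90", provided the subject has not died. That covers withdrawals.

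On how such a subject is analysed, three SAP rules matter.

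- SAP 5.3 analyses the primary safety outcome, stroke-related mortality at 90 days, in the ITT population.
- SAP 6.3 sets the denominator for safety rates as "the number of all Subjects in the study, regardless of their follow-up time".
- SAP 4.8 uses multiple imputation when Day-90 mRS is missing but a Day-30 or Day 5-7 value exists. With no Day 5-7 value either, "if that also missing, the subject will be counted as a failure (mRS 6").

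**The concern.** Protocol 8.3 and SAP 4.8 both ask for near-complete follow-up, above all for Day-90 mRS and mortality. Protocol 6.3 works against that aim, because it stops collection of both when a subject withdraws, including where the subject would have agreed to a telephone call.

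The missing data reach the primary efficacy endpoint, which is analysed in all randomized subjects, and the primary safety outcome, where a death nobody recorded is counted as no death. Assignment is open label (Protocol 5.4), so withdrawal need not be balanced between arms and the error need not cancel. Early withdrawal is foreseeable: outside the U.S. a subject may be enrolled under emergency consent and asked later whether to continue (Protocol 6.1 and 7.1).

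**Working it through.** **Step 1: do the two follow-up rules conflict?** The protocol rule covers withdrawn subjects. The SAP rule covers discontinued subjects, whatever the reason. Since the definition of discontinued includes withdrawals, the difference in terms does not separate them, and the sentence in SAP 4.11 on adverse events names withdrawal directly. The rules conflict.

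**Step 2: is SAP 4.11 consistent on length?** It gives the duration of the study in one sentence and 104 days in the next. The two meet only if the first means the subject's own participation (90 + 14 = 104 days); the SAP does not say so.

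**Step 3: what happens to a withdrawn subject under each rule?**

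| Subject | Protocol 6.3 applied | SAP 4.11 applied |
|---|---|---|
| Withdraws alive before the Day 5-7 mRS | Later death unseen. Safety: non-event by default. Efficacy: mRS 6. | Later death would be recorded. If alive: non-event, now observed. Efficacy: still mRS 6, because safety follow-up supplies no mRS. |
| Withdraws alive after a Day 5-7 or Day-30 mRS | Later death unseen. Safety: non-event by default. Efficacy: multiple imputation. | Later death would be recorded. If alive: observed non-event. Efficacy: multiple imputation. |

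The follow-up conflict decides whether a safety non-event is observed or merely assumed. The split between non-event and mRS 6 appears only in the first row, and it appears under both follow-up rules, so its source is SAP 4.8 plus SAP 6.3.

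**Step 4: size.** No withdrawal rate is stated, so these are assumptions:

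- Withdrawal rate: the loss-to-follow-up rates of three earlier device studies quoted in Protocol 8.3 and SAP 4.8. 4/164 = 2.44%; 6/178 = 3.37%; 11/151 = 7.28% (printed as 7.2%).
- Death rate: 0.19, the control mRS 6 proportion in Protocol Table 6. The printed row sums to 0.99; rescaling gives 0.19/0.99 = 19.2%, which changes nothing here.
- N: 500 (maximum) and 150 (minimum), Protocol 8.1.

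Subjects affected = N × rate. Deaths unseen = subjects × 0.19.

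| N | Rate | Subjects | Deaths, at most |
|---|---|---|---|
| 500 | 2.44% | 12.2 | 2.3 |
| 500 | 7.28% | 36.4 | 6.9 |
| 150 | 2.44% | 3.7 | 0.7 |
| 150 | 7.28% | 10.9 | 2.1 |

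**Step 5: size of the split.** If a share d of an arm has no post-baseline mRS and no recorded death, the mRS 6 rate in efficacy exceeds the recorded all-cause death rate by exactly d. If every lost subject left before Day 5-7, d would be 2.4 to 7.3 percentage points. The actual gap is smaller by the share who have a Day 5-7 or Day-30 mRS.

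**The case against.** The strongest reply accepts that the sentences conflict and disputes what follows from it.

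- *Cause.* A reader might infer that the follow-up conflict produces the non-event/mRS 6 split. It does not: a subject confirmed alive under SAP 4.11 but with no mRS is still scored mRS 6. This objection stands.
- *Scope.* A reader might infer that all withdrawn subjects are scored mRS 6. Only those with no Day 5-7, Day-30 or Day-90 mRS are, and the Day 5-7 assessment is made in hospital or before discharge. This stands too. The score is also a conservative efficacy rule, not a record of death.
- *Size.* A reader might take 2 to 7 missed deaths as an estimate. The rates are for loss to follow-up, which Protocol Section 7 lists separately from withdrawal. The 19% is a full 90-day, all-cause, control-arm figure. Subjects who withdraw are alive at that point and have less than 90 days of risk left, and stroke-related deaths are only a subset. This stands, so the figures serve only as a ceiling on the stated assumptions.
- *Already handled.* SAP 4.15 compares arms on the incidence of and reason for study termination. SAP 6.2 compares subjects with and without data and promises sensitivity analyses. These help describe the missing data but recover none of it. SAP 6.2 also deems imputation necessary only when more than 20% of values are missing and the missingness is associated with key prognostic factors; the quoted loss rates are well below 20%.
- *Unseen text.* The consent template and the Adaptive Design Plan are not in the documents reviewed. Either may say more about data after withdrawal or about imputation. Neither would remove the conflict between Protocol 6.3 and SAP 4.11 as written. Protocol 6.3 does not mention vital status; that its collection stops follows from the rule that there is no additional follow-up.

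**Conclusion.** The concern holds as an inconsistency with a modest effect that the documents do not allow one to quantify. Protocol 6.3 and SAP 4.11 cannot both be followed, and SAP 4.11 leaves the length of follow-up unclear. Under the protocol rule, Day-90 mRS and later deaths in withdrawn subjects are lost, and the SAP 6.3 denominator counts an unseen death as a non-event. Stroke-related mortality could therefore be understated; the documents do not show that it will be.

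The different scoring of an early withdrawal in safety and efficacy is real but separate, and confined to subjects with no post-baseline mRS.

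On the borrowed rates, 12 to 36 subjects and at most about 2 to 7 deaths would be affected at N = 500, or about 4 to 11 subjects and 0.7 to 2 deaths at N = 150. These are upper-bound illustrations that depend on treating withdrawal as if it occurred at the quoted loss-to-follow-up rates. The point should be corrected because it touches both the primary efficacy and the primary safety outcome and the correction is cheap.

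**What to change.** - Reconcile Protocol 6.3 and SAP 4.11 into one rule with one follow-up length, stated identically in both documents.
- Separate stopping study visits from withdrawing consent for data collection. A subject who stops visits is still asked for Day-90 mRS and vital status; Protocol 7.9.2 already permits a telephone mRS. Only withdrawal of consent for data collection ends follow-up.
- Record the type of withdrawal on the CRF.
- Report early withdrawals (before any post-baseline mRS) by arm, and add a sensitivity analysis for stroke-related mortality that does not assume unobserved subjects are non-events.

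The cost is minor protocol and consent wording, one CRF item and one added analysis. It will not recover subjects who cannot be reached, so the sensitivity analysis is needed in any case.
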